# 16.3 APPENDIX C: DIAGNOSTIC CRITERIA OF CHRONIC GVHD

Organ or Site	Diagnostic Features 	Distinctive Features 	Others 	Common Features 
Mouth	Lichen-type features Hyperkeratotic plaques Restriction of mouth opening from sclerosis	Xerostomia Mucocele Mucosal atrophy Pseudomembra nes  Ulcers 		Gingivitis Mucositis Erythema Pain
Eyes		New onset dry, gritty, or painful eyes  Cicatricial conjunctivitis Keratoconjunct ivitis sicca  Confluent areas of punctuate keratopathy	Photophobia Periorbital hyperpigmentation Blepharitis 	
Genitalia	Lichen planus- like features Vaginal scarring or stenosis	Erosions  Fissures  Ulcers 		
Lung	Bronchiolitis obliterans diagnosed with lung biopsy	Bronchiolitis obliterans diagnosed with PFTs  and radiology 		BOOP 
Muscle, Fascia, joints	Fasciitis Joint stiffness or contractures secondary to sclerosis	Myositis or polymyositis	Edema Muscle cramps Arthralgia or arthritis	

Organ or Site	Diagnostic Features 	Distinctive Features 	Others 	Common Features 
Hematopoiet ic and immune				Thrombocytopenia Eosinophilia Lymphopenia Hypo- or hypergammaglobilin emia Autoantibodies (AIHA and ITP) 
Other				Pericardial or pleural effusions Ascites Peripheral neuropathy Nephrotic syndrome Myasthenia gravis Cardiac conduction abnormality or cardiomyopathy

1.Sufficient to establish the diagnosis of cGvHD

2.Seen in cGvHD, but insufficient alone to establish a diagnosis of cGvHD

3.Can be acknowledged as part of the cGvHD symptomatology if the diagnosis is confirmed

4.Seen with both acute and cGvHD

5.Usually symmetric, affects most nails

6.In all cases, infection, drug effects, malignancy, or other causes must be excluded.

7. After recovery from chemoradiation therapy

8.Not explained by endocrine or other causes

9.Diagnosis of cGvHD requires biopsy or radiology confirmation (or Schirmer test for eyes)

10.Erythema of the eyelids with edema

11.Infants and children

12.Pulmonary function tests

13.Bronchiolitis obliterans-organizing pneumonia

**Abbreviated Title:** Pomalidomide for cGvHD **Version Date:** 4/29/2025

14.AIHA: autoimmune hemolytic anemia; ITP: idiopathic thrombocytopenic purpura

Category	Time of Symptoms After HCT or DLI	Presence of Acute GVHD Features	Presence of Chronic GVHD Features 
Acute GVHD			
Classic acute GVHD	$\leq$ 100 days	Yes	No
Persistent, recurrent, or late-onset acute GVHD	> 100 days	Yes	No
Chronic GVHD			
Classic cGvHD	No time limit	No	Yes
Overlap syndrome	No time limit	Yes	Yes

# 16.4 APPENDIX D: CLINICAL DIFFERENTIATION OF ACUTE AND CHRONIC GVHD

1. Abbreviations: HCT: hematopoietic cell transplantation; DLI: donor lymphocyte infusion

2. See Appendix C for features
### 16.5 APPENDIX E: ORGAN SPECIFIC AND GLOBAL SCORING OF CHRONIC GVHD

	SCORE 0	SCORE 1	SCORE 2	SCORE 3		
PERFORMANCE SCORE:	Asymptomatic and fully active (ECOG 0; KPS or LPS 100%)	Symptomatic, fully ambulatory, restricted only in physically strenuous activity (ECOG 1, KPS or LPS 80-90%)	Symptomatic, ambulatory, capable of self-care, >50% of waking hours out of bed (ECOG 2, KPS or LPS 60-70%)	Symptomatic, limited self-care, >50% of waking hours in bed (ECOG 3-4, KPS or LPS <60%)		
Skin	No Symptoms	<18% BSA with	19-50% BSA OR	>50% BSA OR		
Clinical features:		disease signs but NO sclerotic features	involvement with superficial sclerotic	deep sclerotic features "hidebound" (unable to		
Maculopapular rash		Selerence reactives	features "not	pinch) OR impaired		
Lichen planus-like features			pinch)	mobility, ulceration or severe pruritus		
Papulosquamous lesions or ichthyosis						
Hyperpigmentation						
Hypopigmentation						
Keratosis pilaris						
Erythema						
Erythroderma						
Poikiloderma						
Sclerotic features						
Pruritus						
Hair involvement						
Nail involvement						
% BSA						
involved						
Μουτη	No symptoms	Mild symptoms with disease signs but not limiting oral intake significantly	Moderate symptoms with disease signs with partial limitation of oral intake	Severe symptoms with disease signs on examination with major limitation of oral intake		
LIP Print Name:		LIP Signature:				
Date of Evaluation:						
Timepoint: Baseline	Off Study					

#### **Abbreviated Title:** Pomalidomide for cGvHD **Version Date:** 4/29/2025

	SCORE 0	SCORE 1	SCORE 2	SCORE 3
GI TRACT	No symptoms	Symptoms such as dysphagia, anorexia, nausea, vomiting, abdominal pain or diarrhea without significant weight loss (<5%)	Symptoms associated with mild to moderate weight loss (5-15%)	Symptoms associated with significant weight loss >15%, requires nutritional supplement for most calorie needs OR esophageal dilation
LIVER	Normal LFT	Elevated Bilirubin, AP*, AST or ALT <2 x ULN	Bilirubin >3 mg/dl or Bilirubin, enzymes 2-5 x ULN	Bilirubin or enzymes > 5 x ULN
LUNGS*	No symptoms	Mild symptoms (shortness of breath after climbing one flight of steps)	Moderate symptoms (shortness of breath after walking on flat ground)	Severe symptoms (shortness of breath at rest; requiring $0_2$ )
FEV1	FEV1 > 80% OR LFS=2	FEV1 60-79% OR LFS 3-5	FEV1 40-59% OR LFS 6-9	FEV1 ≤39% OR LFS 10-12
EYES Mean tear test (mm): >10 6-10 ≤5 Not done	No symptoms	Mild dry eye symptoms not affecting ADL (requiring eyedrops ≤ 3 x per day) OR asymptomatic signs of keratoconjunctivitis sicca	Moderate dry eye symptoms partially affecting ADL (requiring drops > 3 x per day or punctal plugs), WITHOUT vision impairment	Severe dry eye symptoms significantly affecting ADL (special eyeware to relieve pain) OR unable to work because of ocular symptoms OR loss of vision caused by keratoconjunctivitis sicca
LIP Print Name:		LIP Signature:		
Date of Evaluation: Timepoint: Baseline	Off Study			

	SCORE 0	SCORE 1 SCORE 2		SCORE 3
JOINTS AND FASCIA	No symptoms	Mild tightness of arms or legs, normal or mild decreased range of motion (ROM) AND not affecting ADL	Tightness of arms or legs OR joint contractures, erythema due to fasciitis, moderate decrease ROM AND mild to moderate limitation of ADL	Contractures WITH significant decrease of ROM AND significant limitation of ADL (unable to tie shoes, button shirts, dress self etc.)
GENITAL TRACT	No symptoms	Symptomatic with mild signs on exam AND no effect on coitus and minimal discomfort with gynecologic exam	Symptomatic with moderate signs on exam AND with mild dyspareunia or discomfort with gynecologic exam	Symptomatic WITH advanced signs (stricture, labial agglutination or severe ulceration) AND severe pain with coitus or inability to insert vaginal speculum

\* AP may be elevated in growing children, and not reflective of liver dysfunction

# Other indicators, clinical manifestations or complications related to cGVHD (check all that apply and assign a score to its severity (0-3) based on its functional impact (none – 0,mild -1, moderate -2, severe – 3)

 Pericardial Effusion	آ Pleural Effusion(s)						
آ Nephrotic syndrome	ر Peripheral Neuropathy						
ر Cardiomyopathy	$\int Eosinophilia > 500 \mu l_{}$						
Cardiac conduction defects	 Coronary artery involvement						
 Progressive onset							
LIP Signa	ture:						
Date of Evaluation:							
	 Pericardial Effusion						

Timepoint: Baseline Off Study

When discrepancy exists between pulmonary symptom or PFT scores the higher value should be used for final scoring. Scoring using the Lung Function Score (LFS) is preferred, but if DLCO is not available, grading using FEV1 should be used. The percent predicted FEV1 and DLCO (adjusted for hematocrit but not alveolar volume) should be converted to a numeric score as follows: >80% = 1; 70-79% = 2; 60-69% = 3; 50-59% = 4; 40-49% = 5; <40% = 6. The LFS = FEV1 score + DLCO score, with a possible range of 2-12.

## 16.6 APPENDIX F: GLOBAL SCORING OF CGVHD

Stage	Definition
Mild	Only 1 or 2 organs or site (except the lung) No clinically significant functional impairment (maximum of score 1 in all affected organs or sites)
Moderate	At least 1 organ or site with clinically significant but no major disability (maximum score of 2 in any affected organ or site), or 3 or more organs or sites with no clinically significant functional impairment (maximum score of 1 in all affected organs or sites)
Severe	Major disability caused by cGvHD (score of 3 in any organ or site) Lung function score $\geq 2$

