## 2 ELIGIBILITY ASSESSMENT AND ENROLLMENT

#### 2.1 ELIGIBILITY CRITERIA

#### 2.1.1 Inclusion Criteria

- 2.1.1.1 Moderate or severe cGvHD diagnosed and staged per NIH criteria (Filipovich et al 2005), Appendix C, Appendix D, Appendix E and Appendix F..
- 2.1.1.2 ≥18-75 years of age, because no dosing or adverse event data are currently available on the use of pomalidomide in persons <18 years of age
- 2.1.1.3 Has cGvHD that did not respond to high-dose corticosteroids (average 0.5 mg/kg/d prednisone for ≥8 weeks) or second-line systemic therapy
- 2.1.1.4 If taking systemic therapy for cGvHD at the time of enrollment, must be on a stable or tapering schedule in the preceding 4 weeks (extracorporeal photopheresis has to be stopped at least by 4 weeks before enrollment)
- 2.1.1.5 Karnofsky performance score  $\geq 60\%$  (Appendix A)
- 2.1.1.6 Life expectancy >3 months
- 2.1.1.7 Stable primary malignancy for previous 3 months
- 2.1.1.8 Agree to adhere to methods of contraception and other fertility control measures as prescribed by the protocol
  - Agents of this class are known to be teratogenic, women of child-bearing potential and men must agree to use effective forms of contraception (hormonal or barrier method of birth control; abstinence) prior to study entry and for the duration of study participation. Should a woman become pregnant or suspect she is pregnant while she or her partner is participating in this study, she should inform her treating physician immediately.
  - Female Subjects
    - Females of childbearing potential (FCBP)† must have a negative serum or urine pregnancy test with a sensitivity of at least 25 mIU/mL within 10 14 days prior to and again within 24 hours of starting pomalidomide and must either commit to continued abstinence from heterosexual intercourse or begin TWO acceptable methods of birth control, one highly effective method and one additional effective method AT THE SAME TIME, at least 28 days before she starts taking pomalidomide. FCBP must also agree to ongoing pregnancy testing. Men must agree to use a latex condom during sexual contact with a FCBP even if they have had a vasectomy. All patients must be counseled every 28 days about pregnancy precautions and risks of fetal exposure through the POMALYST REMSTM program. See Appendix M: Risks of Fetal Exposure, Pregnancy Testing Guidelines and Acceptable Birth Control Methods.

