**Eyes:** The primary measurement of lacrimal gland function in cGvHD is using the Schirmer's test. The test should be performed without anesthesia for both eyes (OU) unless physically inapplicable. The measurement of each eye and the average of measurements will be recorded in the CRF.

Mouth: Mouth assessments include:

(1) mucosal erythema by 0-3 grading based on the color intensity, (2) lichen-type hyperkeratosis by 0-3 grading based on the percentage of oral surface area, (3 ulceration by 0-6 based on percentage of oral surface area, and (4) mucoceles by 0-3 grading based on its total number of presence.

Hematopoietic: The measurements of hematopoietic response include:

(1) platelet count,

(2) eosinophil count and percentage.

White blood cell (WBC) count will be recorded on the Assessment Form but will not be used for response assessment.

**Gastrointestinal tract:** Gastrointestinal (GI) symptoms are graded through interview by the investigator according to 0-3 severity scales.

**Liver:** Involvement of liver is graded according to the levels of bilirubin and liver enzymes (AST and ALT).

**Lung:** The forced expiratory volume in the first second (FEV1) and single breath diffusion lung capacity for carbon monoxide (DLCO) is included as components for the lung function score (LFS). LFS is computed by the extent of FEV1 and DLCO compromise (>80% = 1, 70 - 79% = 2, 60 - 69% = 3, 50 - 59% = 4, 40 - 49% = 5, <40% = 6). Scores for FEV1 and DLCO are added and the sum reduced to an overall category according to following table (Table 5). Absolute values of both FEV1 and DLCO should be recorded in the CRF.

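### Appendix F's lung line for severe disease sets a cut-off of 2 on a score the protocol defines as running from 2 (normal) to 12, so as printed it cannot separate normal from impaired lungs

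*Combined protocol and SAP*

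**What the plan says.** Inclusion criterion 2.1.1.1 asks for "Moderate or severe cGvHD diagnosed and staged per NIH criteria" and cites Appendices C to F. Appendix F is the table that turns organ findings into a global stage:

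- Mild: "Only 1 or 2 organs or site (except the lung"), with organ scores no higher than 1.
- Moderate: a "maximum score of 2 in any affected organ or site", or three or more organs at score 1.
- Severe: "score of 3 in any organ or site) Lung function score", the lung part having a cut-off of 2 or more. The available text shows no 'and' or 'or' between the two conditions.

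The lung term is defined elsewhere. In Section 6.2.2.1, FEV1 together with DLCO "is included as components for the lung function score (LFS"), and Table 5 labels a score of 2 as normal. The notes to Appendix E state: "The LFS = FEV1 score + DLCO score, with a possible range of 2-12". The lung row of Appendix E gives organ score 0 to "FEV1 > 80% OR LFS=2". A footnote to Appendix I sets a special progression rule for starting lung function scores of 10 or more, which can exist only on the 2-12 scale. The 0-3 lung organ score has a different name: exclusion 2.1.2.11 calls it the NIH lung score.

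**The concern.** The Severe row borrows a term that the protocol uses consistently for a 2-12 sum, and applies to it the lowest value that the sum can take. A rule met by normal lungs cannot identify severe lung disease.

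Three things depend on the table. Criterion 2.1.1.1 uses it to decide who may enter. Global stage is documented at screening (Section 2.3) and baseline (Section 2.6), and so describes the arms. Section 6.2.2.3 lists NIH global severity among the endpoints to be recorded. That section refers to Appendix P, which contains no staging rule, so Appendix F is the only place where the global stages are defined. With at most 16 patients per arm, a few patients staged on different scales would visibly change the baseline table.

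**Working it through.** **Inputs.** FEV1 and DLCO are each scored 1 (above 80% of predicted) to 6 (below 40%), per Section 6.2.2.1 and the notes to Appendix E. The lung row of Appendix E converts LFS to the organ score: 2 gives 0, 3-5 gives 1, 6-9 gives 2, 10-12 gives 3.

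**The plan's own range.** LFS = FEV1 score + DLCO score. Minimum 1 + 1 = 2; maximum 6 + 6 = 12. The stated 2-12 is reproduced.

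**The printed cut-off on that scale.** There are 6 × 6 = 36 score pairs:

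| LFS | Pairs | Appendix E lung score |
|---|---|---|
| 2 | 1 | 0 |
| 3-5 | 2 + 3 + 4 = 9 | 1 |
| 6-9 | 5 + 6 + 5 + 4 = 20 | 2 |
| 10-12 | 3 + 2 + 1 = 6 | 3 |

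An LFS of 2 or more holds for 36 of 36 pairs. A 0-3 score of 2 or more, taken through the LFS bands alone, holds for 20 + 6 = 26 of 36, that is, for LFS 6 and above. These are counts of score pairs, not proportions of patients.

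**What each reading does.** Patient A has one non-lung organ at score 1 and normal lungs. Patient B has a lung score of 2 through LFS 6-9 and no organ at 3. Exclusion 2.1.2.11 removes lung score 3, so B has the highest lung score that can enter.

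| Reading of the lung line | Patient A | Patient B |
|---|---|---|
| LFS, joined by 'or' | meets Mild and Severe | meets Moderate and Severe |
| LFS, joined by 'and' | Mild | Moderate; the lung line adds nothing |
| 0-3 score, joined by 'or' | Mild | meets Moderate and Severe |
| 0-3 score, joined by 'and' | Mild | Moderate |

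The last reading leaves a gap. A patient with skin score 3 and lung score 0 or 1 would fit no row, because Mild stops at 1 and Moderate at 2. The third reading gives the lung line a purpose without that gap, but B still fits two rows until the table says which one prevails.

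**Where the LFS bands are not the whole rule.** Appendix E takes the higher of the symptom score and the lung-function score, so moderate symptoms alone give a lung score of 2. It also says that "if DLCO is not available, grading using FEV1 should be used", in which case no LFS exists. The FEV1 and LFS bands can differ as well. FEV1 of 55% with DLCO above 80% gives LFS 4 + 1 = 5 (score 1), while that FEV1 lies in the 40-59% band for score 2. Appendix E prefers the LFS there. So a 0-3 score of 2 or more is close to, but not identical with, LFS 6 or more.

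**The case against.** The best defence is that no trained assessor would be misled. Every other threshold in Appendix F is on the 0-3 organ scale. Criterion 2.1.1.1 also cites Appendix E and the published NIH staging criteria. The missing conjunction may be no more than a line break lost when the PDF was read. The population makes mild disease unlikely: entry requires non-response to high-dose corticosteroids or second-line systemic therapy, and Section 1.2.1.2 says systemic therapy is usually for three or more involved organs or an organ score of at least 2. Finally, no planned test, stopping rule or power figure in Section 10 uses global severity, the primary response uses Appendices H and I, and the 0-3 organ scores are collected separately.

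Most of this stands, and it limits the consequences. It does not remove the contradiction: the printed term has one definition in this protocol, and on that definition the threshold is empty.

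A reader might infer more: that every patient is staged severe, that the criterion excludes no one, and that global severity can never improve. The documents do not support this. Those statements need both the LFS reading and an 'or', and no conjunction is visible. Even then patient A also meets the Mild row, which is a conflict to resolve, not proof that staging ends at Severe. Nor can one say that all patients meet the cut-off, since a patient graded on FEV1 alone has no LFS.

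**Conclusion.** The point holds as a wrong or mislabelled threshold in an eligibility and staging rule. On the protocol's own definition the lung cut-off is the minimum possible score, met by 36 of 36 score pairs and so by anyone who has an LFS. Whether this admits mild disease depends on the unstated conjunction. Which stage a patient with lung score 2 receives depends on the scale, the conjunction and an unstated order of precedence.

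The 0-3 lung score of Appendix E is the only scale on which the line does anything, and it matches the rest of the table. That is an inference from the table's structure. The documents do not show which scale the staff used.

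The reach is limited to eligibility staging, the baseline description of the arms, and the recorded global severity endpoint of Section 6.2.2.3. Alpha, power, sample size and the primary endpoint are unaffected.

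**What to change.** Reconcile Appendix F with Appendix E and Table 5 in the Severe row:

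1. Name the scale: the 0-3 lung score of Appendix E, with its rules on symptoms and on FEV1 alone when DLCO is missing.
2. State the conjunction between the two Severe conditions, after checking the NIH staging source that criterion 2.1.1.1 cites. As shown above, 'and' on the 0-3 scale would leave some patients with an organ score of 3 without a stage.
3. State that a patient who meets Severe through the lung line is not staged Moderate. Replacing the term alone would leave a lung score of 2 in both rows.
4. Point Section 6.2.2.3 to Appendix F for global severity.

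Then check that the global severity already recorded, at entry and at later evaluations, used one scale, and restage from the separately collected organ scores where it did not. The cost is a short edit to one table row, one cross-reference, and a review of at most 35 patients' records (the accrual ceiling in Section 10). No new data are needed.

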# 16.7 APPENDIX G: CHRONIC GVHD ASSESSMENT (CLINICIAN) FORM

Current Patient Weight:		Toda	ay's I	Date:			MR	#/N	ame:		
Component	Findings	Findings					Scoring (see skin score worksheet)				
Skin	Erythemato	us rash of	any	sort			% BSA (max 100%)				
	Moveable s	Moveable sclerosis						%	BSA (max 100%)	)	
10 Front	Non-movea subcutaneou	Non-moveable sclerosis (hidebound/non-pinchable) or subcutaneous sclerosis/fasciitis					r % BSA (max 100%)				
	Ulcer(s): s measure its of ulcer	Ulcer(s): select the largest ulcerative lesion, and measure its longest dimension in cm and mark location of ulcer					Location:				
							Longest dime	ensi	on:ci	n	
Eyes Bilateral Schirmer's Tear Test (without anesthesia) in persons 9 years or older	t Right Eye: wetting			mm of	Le	eft Eye: etting				mm	of
Mouth	Mucosal change	No evi of CGVH	dence ID	e Mild		Mo	derate		Severe		
	Erythema	None	0	Mild erythema moderate eryther (<25%)	or ma	1 Mo or eryt	derate (≥25%) Severe hema (<25%)	2	Severe erythem (≥25%)	a 3	

Hard Palate Pharynx Pharynx Tongue		Lichenoid	None	0	Hyperkeratotic changes(<25%)	1	Hyperkeratotic changes(25-50%)	2	Hyperker changes (2	ratotic >50%)	3
		Ulcers	None	0	None	0	Ulcers involving (≤20%)	g 3	Severe ulceration (>20%)	18	6
		Mucoceles*	None	0	1-5 mucoceles	1	6-10 scattered mucoceles	2	Over mucocele	10 s	3
					*Mucoceles scored lower labial and palate only	d fo sof	r t		Total sc all changes	ore for mucosal	
											·
Blood Counts	Platelet (K/uL)	Count U	LN (K/uL)		Total WBC (K/uL)	UL	N (K/uL)	]	Eosinophil	s (% )	
Liver Function Tests	Total bilirubin (r	serum U ng/dL)	LN (mg/dI	.)	ALT (U/L) U	JLN	(U/L) Alkaline Phospha	tase	(U/L) [	ULN (U/I	L)
Gastrointestinal-	U pper GI	0= no symp	toms	1			I		1		
• Early satiety OR		l=mild, occ	casional syn	mpt	oms, with little redu	ction	in oral intake duri	ng tl	he past wee	ek	
• Anorexia OR		2=moderate	e, intermitte	ent ,	symptoms, with som	e red	uction in oral intak	e du	uring the po	ast week	

Nausea & Vomiting	3=more severe or persistent symptoms throughout the day, with marked reduction in oral intake, on almost every day of the past week								
Gastrointestinal- Esophageal • Dysphagia OR • Odynophagia	
 
0= no esophageal symptoms
 
1=Occasional dysphagia or odynophagia with solid food or pills during the past week
 
2=Intermittent dysphagia or odynophagia with solid foods or pills, but not for liquids or soft foods, during the past week
 
3=Dysphagia or odynophagia for almost all oral intake, on almost every day of the past week
 
								
Gastrointestinal-Lower GI	0= no loose or liquid stools during the	0= no loose or liquid stools during the past week							
• Diarrhea	l = occasional loose or liquid stools,	on some days during the past we	ek						
	2=intermittent loose or liquid stools throughout the day, on almost every day of the past week, without requiring intervention to prevent or correct volume depletion								
	3=voluminous diarrhea on almost ev correct volume depletion	very day of the past week, requir	ing intervention to prevent or						
Lungs • Bronchiolitis Obliterans	Pulmonary Function Tests with Diffusing Capacity (attach report for person> 5 yrs old)	FEV-1	Single Breath DLCO (adjusted for hemoglobin)						
		(% Predicted)	(%Predicted)						
Health Care Provider Global Ratings: In your opinion, do you	IealthCareProviderWhere would you rate the severity of this patient's cGvHGlobal Ratings:symptoms on the following scale, where 0 is CGVHD symptorthat are not at all severe and 10 is the most severe CGVH								
think that this patient's	symptoms possible:		+3= Very much better						
cGvHD is mild, moderate or			+2= Moderately better						
0=none	0 1 2 3 4 5 6	7 8 9 10	+1 = A little better						
			0= About the same						

1= mild	cGvHD sy	mptoms	cGvHD	symptoms	-1=A little worse				
2=moderate	not at all s	evere	mos nossik	st severe	-2=Moderately worse				
3=severe			PUSSIC		-3=Very much worse				
Karnofsky Performance	Score	Performance Status Scale Definitions (Use Lansky Play Performance for person 16 years old)							
Able to carry on normal	100	Normal no complaints; no ev	idence of dise	ase					
special care needed.	90	Able to carry on normal activ	Able to carry on normal activity; minor signs or symptoms of disease						
	80	Normal activity with effort; s	symptoms of d	isease					
Unable to work; able to live at	70	Cares for self; unable to carry on normal activity or to do active work							
personal needs; varying	60	Requires occasional assistance but is able to care for most personal needs							
amount of assistance needed.	50	Requires considerable assistance and frequent medical care							
Unable to care for self;	40	Disabled; requires special care and assistance							
institutional or hospital care;	30	Severely disabled; hospital admission is indicated although death not imminent							
disease may be progressing rapidly.	20	Very sick; hospital admission necessary; active supportive treatment necessary							
	10	Moribund; fatal processes progressing rapidly							
	0	Dead							

Organ and Starting Score or Value at Baseline	Partial Response Criterion 
Skin (% of BSA)	
> 50	$e/s \le 0.5$ and $e > 0$
25-50	$s - e \ge 25$ and $e > 0$
< 25	Only CR; no PR possible
Eye (mm Schirmer's test)	
< 5 mm	$e - s \ge 5 mm$ and $e < LLN$
5-10 mm	Only CR; no PR possible
Mouth (Schubert Scale 0-15)	
> 8	$e/s \le 0.5$ and $e > 0$
4 – 7	$s - e \ge 4$ and $e > 0$
< 4	Only CR; no PR possible
Hematology	
Platelet count	$e - s \ge 100,000/\mu L$ and $e < LLN$
Eosinophil count	
$\geq$ 3 X ULN	$e/s \le 0.5$ and $e > ULN$
< 3 X ULN	Only CR; no PR possible
Gastrointestinal (0-3 scales)	
3	e = 1 or 2
2	e = 1
1	Only CR; no PR possible
Liver function	
(ALT, alkaline phosphatase and bilirubin)	
$\geq$ 3 X ULN	$e/s \le 0.5$ and $e > ULN$
< 3 X ULN	Only CR; no PR possible

